7.2.4 Premature Patient Discontinuation from the Study

Patients are free to withdraw consent and/or discontinue participation in the study at any time, without prejudice to further treatment. A patient's participation in the study may also be discontinued at any time at the discretion of the Investigator.

Patients who are prematurely withdrawn from the study will be asked to complete all discontinuation assessments prior to withdrawal, if possible. Post-study serious adverse events (SAEs) will be reported according to Section 8 and 9. A patient will be considered early terminated if the patient does not complete the study after enrollment.

Patients who are withdrawn from the study will not be replaced (i.e., a patient's study number will not be reused); however, additional patients may be enrolled to offset patient dropouts.

7.3 Patient Population and Selection

A total of 45 patients are planned to be enrolled in the study. 15 patients will be randomized into 3 groups on the basis of the MUSCULAR IMPAIRMENT RATING SCALE (MIRS) age and gender.

7.4 In- and Exclusion Criteria

7.4.1 Inclusion criteria

A patient must meet all of the following criteria to be eligible for this study:

1. The patient is willing and able to provide signed informed consent.
2. The patient is ≥ 18 years of age.
3. The diagnosis myotonic dystrophy type 1 has been confirmed by molecular genetics.
4. The patient is able and willing to perform pulmonary lung function tests (PFT) throughout the entire study as well as capillary blood draws for oximetry, fill in a diary and answer questionnaires.

7.4.2 Exclusion criteria

[figure not shown]
A patient who meets any of the following criteria will be excluded from the trial or not randomized to the trial:

1. the patient requires invasive ventilation (non-invasive ventilation is allowed).
2. the patient uses non-invasive ventilation longer than 16h/day.
3. the patient participates in another clinical trial using investigational treatment.
4. the patient cannot perform pulmonary function tests (PFT).
5. the patient is diagnosed with central sleep apnea in polysomnography and not sufficiently treated with NIV ventilation.
6. the patient is diagnosed with obstructive sleep apnea and not sufficiently treated with NIV ventilation.
7. the patient cannot meet the requirements of the study, according to the investigator.
8. the patient is unable to complete a 6-minute walking test.

7.5 Respiratory Muscle Training (RMT)

Respiratory muscle training (RMT) is known and established in patients with chronic obstructive pulmonary disease (COPD) (Borge, Hagen et al. 2014). Several publications point to a positive effect on patients with neuromuscular diseases studied in small populations in patients with amyotrophic lateral sclerosis, Duchenne muscular dystrophy, Pompe disease and myotonic dystrophy (Jones, Crisp et al. 2014, Ferreira, Costa et al. 2016, Jones, Crisp et al. 2016).

Myotonic dystrophy type 1 affects both inspiratory and expiratory muscles. Group 1 patients will perform inspiratory muscle strength training (IMT) in this study. Group 2 patients will perform inspiratory muscle endurance training. Both serve to improve ventilation by increasing respiratory coordination, endurance and strength. Using the "Respifit S®" training device, the two study groups can be treated with different training programs. The "Respifit S®" respiratory therapy device was chosen as it can train both, the strength and endurance of the respiratory muscles, in two separate programs and enables an evaluation of the successfully completed and unsuccessfully completed training sessions. The latter is necessary for the assessment of the efficacy of the respiratory training on completed training units. In addition, compliance can be evaluated. The complete RespifitS®-System contains a patient handset, a digital device displaying patient's efforts and remaining training series and an electronic patient identity card storing patient's trainings and results.

7.5.1 Respiratory Endurance Training

The Respifit S® offers a pressure measurement working as feedback control during inspiration, which is visually displayed to the test person. In endurance mode, the respondent breathes in

and out regularly through the hand set with the aim that a balloon on the screen is held for 60 seconds in the middle part of the screen. The inhalation resistance is determined by the predetermined respiratory minute volume of the test person. The training consists of 7 intervals (1 min each) with pauses of 1 min each. The training should be carried out at least 5 days a week. Patients are asked to fill in a diary of their training sessions. After each training session, patients are asked to indicate how strenuous their breathing training was using the BORG scale (Borg 1982).

7.5.2 Respiratory Strength Training

Patients perform the most common resistance training. A pressure-loaded inhalation valve and an unloaded exhalation flap valve only increase inhalation resistance, which provides a training of the inspiratory muscle strength. The resistance value of the inspiration valve is initially set to 30% of the maximum inspiratory pressure (MIP) measured at the beginning of the study. The intensity will be increased monthly by 10-20%, depending on the individual subjective exertion measured on the BORG scale (Borg 1982). The training consists of 7 intervals (2min) with 6 breaks (1min) in between. Patients should take 15 breaths at each interval. Training should be performed at least 5 days a week. Patients are asked to fill in a diary about their training sessions.

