5. the patient is diagnosed with central sleep apnea in polysomnography and not sufficiently treated by NIV ventilation.
6. the patient is diagnosed with obstructive sleep apnea and is not sufficiently treated with NIV ventilation.
7. the patient cannot meet the requirements of the study, according to the investigator.

STUDY PROCEDURES:

After provided consent to participate in the study, the following diagnostic procedures will be performed:

- At screening, the eligibility of the patient is evaluated and the allocation to one of the two treatment groups (1, 2) or the "placebo group" (3) without respiratory muscle training will be done.
- At baseline, all patients will be assessed for a respiratory function status with FVC, FEV1, MIP, MEP, capillary blood gas analysis, 6-minute walking test including oxygen saturation and questionnaires ("DM1-Activ", "Respicheck" and "FDSS-Fatigue and Daytime Sleepiness-Scale") as well as a clinical examination (including MIRS).
- Patients of the groups 1 and 2
 - will perform a respiratory muscle training (IMT, inspiratory muscle training) for nine months.
 - During training (between months 3 and 9), inspiratory resistance will be increased at each visit (10-20% of baseline MIP), measured by the Borg scale.
 - Patients will be asked fill in a diary about their performed respiratory muscle training
- Patients of group 3 will not perform respiratory muscle training.
- At every visit, all patients will perform the following assessments every two months:
 - Pulmonary function tests, including FVC, FEV1, MIP, MEP (6 times including screening visit)
 - Functional assessments (6-minute walk test + Borg scale at screening, month 1, month 5 and month 9).
 - Clinical examination including MIRS at screening and month 9.
 - Patients are asked to complete the following questionnaires at defined times: three questionnaires on health status in myotonic dystrophy type 1, effects of fatigue and daytime fatigue on everyday life and one questionnaire on clinical symptoms of respiratory insufficiency (DM1-ACTIV, FDSS - FATIGUE AND DAYTIME SLEEPINESS SCALE und RESPICHECK).

STATISTICAL METHODS:

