6 STUDY OBJECTIVES

The primary objective of this study is to determine the safety of repetitive respiratory muscle training on respiratory muscle strength as measured by MIP (maximum inspiratory pressure) in the upright position.

The secondary objectives are to evaluate the

- efficacy and safety of repetitive inspiratory strength respiratory muscle training in 15 patients with myotonic dystrophy type 1,
- efficacy and safety of repetitive inspiratory endurance respiratory muscle training in 15 patients with myotonic dystrophy type 1,
- Measurement of the effect on the quality of life and muscular performance in patients with myotonic dystrophy type 1 during respiratory muscle training or in patients without respiratory muscle training, using the questionnaires "DM1-Activ", "Respicheck" and "FDSS-Fatigue and Daytime Sleepiness-Scale",
- Measurement of the effect on the values CO₂ and O₂ in capillary blood gas analysis of patients with myotonic dystrophy type 1 during respiratory muscle training or in patients without respiratory muscle training,
- Measurement of the effect on muscular endurance performance in patients with myotonic dystrophy type 1 during respiratory muscle training or in patients without respiratory muscle training, measured by the 6-minute walking test.

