8.3.6 Clinical Laboratory Tests (blood analysis)

At the initial examination and every two months a capillary blood analysis will be performed, using epoc blood analysis system, which consists of epoc® BGEM Test Card, epoc® Host2 Mobile Computer and epoc® Care-FillTM Capillary Tubes. Calibration will be done as recommended in users' manual. The Care-Fill™ Capillary Tubes are designed to collect a blood sample from a skin puncture. The tube fills with a blood sample through a combination of capillary action and gravity flow. When sufficient blood is present, the tube fills readily and preserves the integrity of the blood sample until it can be tested by preventing clotting and alteration of analytic concentrations. For each blood draw, approx. 90µl are needed for sufficient analysis. In total, approx. 540µl are drawn per patient during the whole study. The following parameters will be measured: pH, pCO2, pO2.

Observed measurements and changes from baseline to study time points in month 1,3,5,7 and 9 will be descriptively summarized. All laboratory values will be classified as normal, above normal, or below normal based on normal ranges provided by the laboratory. Frequencies of abnormal values and clinically significant abnormal values will be summarized. All data will be presented in listings along with individual listings of patients with clinically significant abnormal laboratory values.

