11.6 Clinical Study Report

A final clinical study report will be produced after study completion.

12 APPENDIX A: Schedule(s) of Study Events

Group 1 and 2:

	Visit 1 Screening month 0	Visit 2 follow-up month 1	Visit 3 follow-up month 3	Visit 4 follow-up month 5	Visit 5 follow-up month 7	Visit 6 final examination month 9
Informed consent	x					
Randomization	x					
Clinical examination including MIRS (Muscular Impairment Rating Scale)	x					x
Pulmonary function test (PFT), sitting and supine	x	x	x	x	x	x
Collection of historical data, especially polysonography and lung function	x					
Maximal expiratory pressure (MEP)	x	x	x	x	x	x
Maximal inspiratory pressure (MIP)	x	x	x	x	x	x
Blood gas analysis (capillary: pO ₂ , pCO ₂ , pH, Hb)	x	x	x	x	x	x
6-minute-walk-test including BORG-scale prior to and after test	x	x		x		x
questionnaire DM1-Activ	x	x	x	x	x	x
questionnaire FDSS (fatigue and daytime sleepiness)	x	x	x	x	x	x
questionnaire "Respicheck" for respiratory insufficiency	x	x	x	x	x	x
Check of patient diary		x	x	x	x	x
Check of data of respiratory training (Respifit S -training device)		x	x	x	x	x
adverse events (AE)		x	x	x	x	x
Instructions for the use of the training device	x	x	x	x	x	x
Increase of resistance by 10%-20%, individually according to BORG scale	start: 30% of MIP	x	x	x	x	

Group 3:

	Visit 1 Screening month 0	Visit 2 follow-up month 1	Visit 3 follow-up month 3	Visit 4 follow-up month 5	Visit 5 follow-up month 7	Visit 6 final examination month 9
Informed consent	X					
Randomization	X					
Clinical examination including MIRS (Muscular Impairment Rating Scale)	X					X
Collection of historical data, especially polysomnography and lung function	X					
Pulmonary function test (PFT), sitting and supine	X			X		X
Maximal expiratory pressure (MEP)	X			X		X
Maximal inspiratory pressure (MIP)	X			X		X
Blood gas analysis (capillary: pO ₂ , pCO ₂ , pH, Hb)	X			X		X
6-minute-walk-test including BORG-scale prior to and after test	X			X		X
questionnaire DM1-Activ	X			X		X
questionnaire FDSS (fatigue and daytime sleepiness)	X			X		X
questionnaire "Respicheck" for respiratory insufficiency	X			X		X
Check of patient diary						
Check of data of respiratory training (Respifit S -training device)						
adverse events (AE)		X	X	X	X	X
Instructions for the use of the training device						
Increase of resistance by 10%-20%, individually according to BORG scale						

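### The protocol gives three schedules for raising training resistance, names the base of the percentage only once, and shows a shared starting load that conflicts with the endurance-arm text

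*Protocol*

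**What the plan says.** Four places in the protocol describe how training resistance is set or raised.

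- **Section 7.5.2 (strength arm).** The start is 30% of the MIP measured at study start. Then: "The intensity will be increased monthly by 10-20%, depending on the individual subjective exertion measured on the BORG scale". The base of the percentage is not given.
- **Synopsis, study procedures, under groups 1 and 2 together.** "During training (between months 3 and 9), inspiratory resistance will be increased at each visit (10-20% of baseline MIP", again with reference to the Borg scale.
- **Appendix A, the table for groups 1 and 2.** The row "Increase of resistance by 10%-20%, individually according to BORG scale" is marked at months 1, 3, 5 and 7 and is blank at month 9. Its month-0 cell reads "start: 30% of MIP". The base of the increase is not given.
- **Section 7.5.1 (endurance arm).** "The inhalation resistance is determined by the predetermined respiratory minute volume of the test person". This section mentions neither a percentage of MIP nor stepwise increases. It does collect an exertion rating: "After each training session, patients are asked to indicate how strenuous their breathing training was using the BORG scale".

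The training arms have follow-up visits at months 1, 3, 5, 7 and 9 (Appendix A). Section 8.3.6 uses the same time points.

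**The concern.** The timing rules exclude one another. The first increase falls at month 1 or at month 3 depending on where one looks, and a monthly rule calls for steps at months 2, 4, 6 and 8, when no visit is scheduled and no procedure for a step is described. The base of the percentage is missing from two of the three places that state an increase. For the endurance arm, the start in Appendix A and the determinant in Section 7.5.1 are different quantities.

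Section 6 states: "The primary objective of this study is to determine the safety of repetitive respiratory muscle training". It also lists strength and endurance training as separate secondary objectives. Adverse events and changes in lung function will be read against the training each arm was meant to receive. If the planned intensity depends on which section was followed, a reader of the results cannot say which regimen was tested.

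**Working it through.** The protocol states no final load and no number of steps, so there is no figure to reproduce. The check sets the texts side by side and then works out what each would imply.

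**1. The texts compared**

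| Place | Arms | Start | When raised | Base of the 10-20% |
|---|---|---|---|---|
| Section 7.5.2 | strength | 30% of MIP | monthly | not stated |
| Synopsis | both | not stated | each visit, months 3 to 9 | baseline MIP |
| Appendix A | both | 30% of MIP | months 1, 3, 5, 7 | not stated |
| Section 7.5.1 | endurance | from respiratory minute volume | not mentioned | not applicable |

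**2. Number of steps, n**

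- Monthly: n = 8, assuming months 1 to 8.
- Appendix A: n = 4.
- Synopsis: n = 3 (months 3, 5, 7), or 4 if a step at month 9 is counted. Training lasts nine months, so a month-9 step would add no training time.

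**3. Nominal final load, as % of baseline MIP**

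The start is 30 and the step s is 0.10 or 0.20. Every step is assumed taken at that size, before any Borg tailoring. Base A is the only one stated, and only in the synopsis. B and C are assumed readings of the unqualified percentage.

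- A, step as % of baseline MIP: 30 + 100 × s × n
- B, step as % of the current setting: 30 × (1 + s)^n
- C, step as % of the starting setting: 30 × (1 + s × n)

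| Base | n = 3 | n = 4 | n = 8 | ratio 8:3 | ratio 8:4 |
|---|---|---|---|---|---|
| A | 60 / 90 | 70 / 110 | 110 / 190 | 1.83 / 2.11 | 1.57 / 1.73 |
| B | 39.9 / 51.8 | 43.9 / 62.2 | 64.3 / 129.0 | 1.61 / 2.49 | 1.46 / 2.07 |
| C | 39 / 48 | 42 / 54 | 54 / 78 | 1.38 / 1.62 | 1.29 / 1.44 |

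Each cell gives 10% steps / 20% steps. With the same base throughout, the monthly rule ends 1.3 to 2.5 times higher than the other schedules.

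**4. Average load over nine months, base A**

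- Monthly: (30 + 40 + … + 110)/9 = 70. With 20% steps, (30 + 50 + … + 190)/9 = 110.
- Appendix A: (30 + 2 × (40 + 50 + 60 + 70))/9 = 470/9 = 52.2. With 20% steps, (30 + 2 × (50 + 70 + 90 + 110))/9 = 670/9 = 74.4.
- Synopsis, n = 3: (3 × 30 + 2 × (40 + 50 + 60))/9 = 390/9 = 43.3. With 20% steps, (90 + 2 × (50 + 70 + 90))/9 = 510/9 = 56.7.

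Monthly against Appendix A is 1.34 / 1.48, and monthly against the synopsis is 1.62 / 1.94. Appendix A against the synopsis is 1.21 / 1.31.

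**5. Effect of the unstated base**

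For the monthly rule alone, A against C is 110/54 = 2.04 and 190/78 = 2.44. Now keep the synopsis on its stated base with n = 3 and give Section 7.5.2 another reading. Under B the monthly rule ends at 64.3/60 = 1.07 or 129.0/90 = 1.43 times the synopsis load. Under C it ends at 54/60 = 0.90 or 78/90 = 0.87 times. So even the direction of the difference depends on the base.

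**The case against.** The timing conflict is not open to dispute, but the rest can be challenged.

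- **The base is an omission, not a contradiction.** No place states a base other than baseline MIP, and Section 7.5.2 gives its start as a percentage of the same quantity. This stands. Readings B and C are scenarios, and the ratios that rest on them should carry less weight than those on base A.
- **Final loads overstate the difference in exposure.** This stands in part. On time-averaged load the factors are smaller, but on the stated base they remain at about 1.3 to 1.9.
- **Several nominal loads exceed the patient's own baseline maximum, so they would not be delivered as computed.** This is true. Borg tailoring and single-centre conduct may bring actual loads closer together. But tailoring governs the individual step. It does not say when a step is due, what the percentage refers to, or which arm it covers.
- **The Appendix A cell may be shorthand in a merged table.** This is possible, since Section 7.5 describes two separate programmes, and Section 7.5.1 does not say that it describes a starting value. But the synopsis also applies the MIP-based increase to both groups, so layout alone does not explain it. On progression Section 7.5.1 is simply silent.
- **The trial is exploratory and no analysis uses the planned load.** This is correct, and it limits the consequence to how the intervention is defined and how its safety is interpreted.

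**Conclusion.** The concern holds. The current text has three incompatible schedules for raising resistance, with 8, 4 or 3 planned steps. On the only stated base, the monthly rule gives a nominal final load 1.6 to 2.1 times that of the other schedules and a nine-month average 1.3 to 1.9 times theirs. The base is missing from Section 7.5.2 and Appendix A, and the shared 30%-of-MIP start does not agree with Section 7.5.1 for the endurance arm.

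These sizes assume monthly steps at months 1 to 8, a 30% start and every step taken in full. They show how far the texts diverge and do not predict delivered loads. The point should be corrected. It does not affect any planned inference, because none is planned.

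**What to change.** Reconcile the synopsis, Sections 7.5.1 and 7.5.2 and Appendix A into one statement of three things: when increases occur, what the percentage is taken of, and which arm or arms the start and the increases apply to. If the arms differ, split the Appendix A row by arm. If monthly increases are kept, describe how they are made in months without a visit. Which rule is right is for the sponsor and investigator to decide, and none is proposed here.

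Optionally, add the resistance set, by visit and arm, to the training summary in Section 10.5. Device data are already checked at visits, but Section 7.5 does not say whether the resistance setting is among the stored items, so that needs confirming first.

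The cost is a short amendment harmonising four places. The reconciliation itself needs no new data. A procedure for between-visit increases has to be written only if the reconciled text calls for them.

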7.6 Training Discontinuation

A patient's study participation may be discontinued at any time at the patient's request or at the discretion of the Investigator. The following may be justifiable reasons for the Investigator to discontinue a patient from treatment:

- The patient was erroneously included in the study (i.e., was found to not have met the inclusion/exclusion criterion).
- The patient experiences an intolerable or unacceptable AE.
- The patient is unable to comply with the requirements of the protocol.
- The patient participates in another investigational study without the prior written authorization of the investigator.
- The patient becomes lost to follow-up.

Discontinuation of treatment does not imply withdrawal from the study, if applicable, the patient is suitable for admission to the control group. The investigator will document the reason(s) for treatment discontinuation on the CRF. Additional patients may be enrolled to offset effects of premature discontinuations.

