All patients who participate in this study will be included in the analysis. Data collected in this study will be documented using summary tables, figures, and patient data listings. For continuous variables, descriptive statistics (n, mean, median, standard deviation, minimum, and maximum) will be presented. For categorical variables, frequencies and percentages will be presented. Graphical displays will be presented as appropriate.

Power and Sample Size:

This is an exploratory study about efficacy and safety of respiratory muscle training in patients with Myotonic Dystrophy Type 1 and is not powered to make other statistical inferences.

Analysis-Sets:

Full Analysis Set: This analysis set consists of all patients who performed respiratory muscle therapy for at least 9 months or who did the check-ups throughout the 9 months without respiratory muscle training. All analyses will be based on this analysis set

Demographics and Baseline Characteristics:

Demographic and baseline data on medical/surgical history and disease history including length of repeats will be summarized using descriptive statistics for continuous variables and frequency distribution for categorical variables.

Safety:

A deterioration of >15% of FVC in comparison with baseline measurements will be defined as an AE, as well as developing unusual myalgia of respiratory muscles for more than 12 hours. The Adverse events will be collected from enrollment (=signed informed consent) through month 9 plus 7 days. Adverse events will be coded using the Medical Dictionary for Regulatory Activities, and categorized by system organ class and preferred term. All AEs will be displayed in patient listings. Adverse events will be categorized and tabulated for the treatment group overall by severity, seriousness, and relationship to study treatment

Efficacy:

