7 INVESTIGATIONAL PLAN

This is a monocentric, three-arm, controlled interventional study for patients with myotonic dystrophy type 1. The patient is not blinded regarding his group assignment (group 1 and 2: respiratory muscle therapy, group 3 control group without respiratory muscle therapy). The patient must provide signed informed consent prior to the study. Suitable patients will either perform

- (a) A nine-month strength training of respiratory muscles (group 1: strength training); or
- (b) A nine-month endurance training of the respiratory muscles (group 2: endurance training);
- (c) Or will not perform any respiratory muscle training for nine months (Group 3: control group).

Lung function tests (FVC, FEV1, MIP, MEP), capillary blood gas analysis (pO₂, pCO₂), 6-minute walking tests, oxygen saturation, and patient questionnaires on quality of life and respiratory symptoms are performed on scheduled visits throughout the entire treatment period. Adverse events (AE) and concomitant medication / therapies will continuously be monitored throughout the whole study. Patients who must be excluded from the trial for safety reasons or who withdraw their participation will not be replaced (i.e. a patient's study number will not be reused); however, it is planned to recruit additional patients if patients terminate participation prematurely.

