7.8 Blinding and Randomization

This is a controlled, randomized, three-arm interventional study on the safety and efficacy of repetitive respiratory muscle training in patients with myotonic dystrophy type 1. As the disease is quite rare and the study is performed as pilot study, with 15 patients included in each group. The randomization software "Randoulette" of the LMU Munich is used for the randomization. The patients will be randomized in 3 groups of 15 patients each, age-, gender- and symptom-corrected according to the MUSCULAR IMPAIRMENT RATING SCALE (MIRS).

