13 APPENDIX B: RANDOMIZATION IN STUDY GROUPS

The Randomization Software "Randoulette" of the LMU Munich is used for the randomization. The patients are randomized in 3 groups of 15 patients each, age-, gender- and symptom-corrected according to the MUSCULAR IMPAIRMENT RATING SCALE (MIRS):

Group 1	Group 2	Group 3
Inspiratory strength training	Inspiratory endurance training	No respiratory muscle training
N = 15	N = 15	N = 15

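### Section 7.6 lets patients who stop training be admitted to the control group, which conflicts with the definition of group 3, and the analysis-set wording does not say how to count them

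*Protocol*

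**What the plan says.** Section 7.6 lists possible reasons for ending a patient's training, among them an intolerable adverse event and inability to comply with the protocol. It then adds: "Discontinuation of treatment does not imply withdrawal from the study, if applicable, the patient is suitable for admission to the control group".

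Section 7 names one control group only. Its patients "will not perform any respiratory muscle training for nine months (Group 3: control group"). Membership is by randomisation: Section 7.8 says "The patients will be randomized in 3 groups of 15 patients each", and Appendix B repeats this. Both add balancing for age, gender and MIRS.

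The Synopsis makes two statements about who is analysed:

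- Under statistical methods: "All patients who participate in this study will be included in the analysis".
- Under analysis sets, the Full Analysis Set has two limbs. The first admits "all patients who performed respiratory muscle therapy for at least 9 months". The second is for untrained patients, those "who did the check-ups throughout the 9 months without respiratory muscle training". On its scope, the Synopsis adds: "All analyses will be based on this analysis set".

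Section 10.6 plans summary statistics and 95% confidence intervals for change from baseline at each visit. Section 10.1 rules out formal tests.

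**The concern.** A patient who has trained for some months and then stopped is not someone who did no training for nine months. Admitting that patient to the control group therefore contradicts the definition of the group. It also means that a group formed by randomisation could gain members because of something that happened later, namely poor tolerance or poor compliance. Those features may well be related to the change in respiratory measures.

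The analysis-set wording should say where such a patient is counted, but its two statements pull in opposite directions. Depending on which is followed, stoppers either sit in the control summaries or vanish from every analysis.

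What is at stake is the descriptive comparison: group means and confidence intervals of change, including change in MIP, the measure named in the primary objective. With no formal test planned, type I error and power are not at issue.

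**Working it through.** **The plan's own figure.** 3 groups × 15 = 45, which agrees with the planned enrolment in Section 7.3. Section 10.2 says that no formal sample size calculation was made, so there is no power figure to reproduce.

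**Step 1: does a stopper fit any category?** Take a patient who starts training and stops at one of the follow-up visits.

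| Stops at month | Trained at least 9 months? | Untrained months left | Untrained for all 9 months? |
|---|---|---|---|
| 1 | no | 9 − 1 = 8 | no |
| 3 | no | 9 − 3 = 6 | no |
| 5 | no | 9 − 5 = 4 | no |
| 7 | no | 9 − 7 = 2 | no |

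Such a patient meets neither limb of the Full Analysis Set, nor the definition of group 3. A fresh nine-month control period is not described. It would also not fit Section 7.2.3, which sets participation at 9 months plus 7 days from consent.

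**Step 2: what follows under each reading?**

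- *Counted as controls.* This needs the all-participants sentence of the Synopsis together with a literal Section 7.6.
- *Dropped.* This follows if the Full Analysis Set governs all analyses.
- *Followed up without training and summarised as randomised.* Section 7.6 then causes no bias.

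**Step 3: illustration of size.** The protocol gives no stopping rate and no SD, so these inputs are assumptions: k = 1 to 3 stoppers per training arm of 15; their mean change m = −0.5 to −1 SD; overall mean 0 in every arm (no true training effect).

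- Training mean once stoppers leave: −m·k/(15 − k)
- Control mean if stoppers from both training arms are counted there: 2k·m/(15 + 2k)
- Control mean if stoppers are dropped: 0

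| k | m | Training mean | Control mean if counted there | Difference if dropped | Difference if counted as controls |
|---|---|---|---|---|---|
| 1 | −0.5 | 0.5/14 = +0.0357 | −1/17 = −0.0588 | 0.0357 | 0.0945 |
| 2 | −1 | 2/13 = +0.1538 | −4/19 = −0.2105 | 0.1538 | 0.3644 |
| 3 | −1 | 3/12 = +0.2500 | −6/21 = −0.2857 | 0.2500 | 0.5357 |

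So the shift is 0.04 to 0.25 SD if stoppers are dropped and 0.09 to 0.54 SD if they are counted as controls. In the second case, 2 of 17 (12%) to 6 of 21 (29%) of those summarised as controls were not randomised to control.

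Only the fall in the control mean, 0.06 to 0.29 SD, comes from Section 7.6 itself. The rest comes from removing stoppers from the training arms, which the Full Analysis Set does on its own. The formulas are linear in m, so stoppers who did better than average would reverse the sign.

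**The case against.** The clause is conditional and permissive, and it follows a statement that stopping training is not withdrawal from the study. It can fairly be read as continued follow-up without training, which is harmless. This stands as a possible reading, but the sentence speaks of admission to the control group and nothing limits it to follow-up. An unseen SAP could settle how patients are grouped in the analysis. It would not remove a contradiction between two protocol sections on who belongs to group 3.

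The conflict within the Synopsis between all participants and completers would also exist without Section 7.6. That is correct. Being followed as a control and being outside an analysis set are compatible, so changing Section 7.6 alone would not cure the shift from dropping stoppers. The two texts need to be corrected together.

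A reader might infer more than the documents support:

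- *That the control summaries will be off by up to 0.54 SD.* That figure needs a reading which the stated Full Analysis Set excludes. It also rests on assumed inputs and measures a between-arm difference that no section specifies as an estimate. With a real training effect, part-trained patients could carry benefit into the control group and offset the shift.
- *That the safety tables by arm are corrupted.* The Synopsis tabulates adverse events for the treatment group overall, and Section 9 lists them for all patients. No section says that an event during training would be counted under control.
- *That Sections 7.9 and 8.4 add further contradictions.* They do not. Section 8.4 concerns the collection of safety data. Section 7.9 can be met by the accountability and compliance summaries in Sections 10.4 and 10.5.
- *That a mover would lose a known number of lung function visits.* The Appendix A table for group 3 shows testing at screening and months 5 and 9, but the Synopsis gives all patients six tests. Any count rests on one side of that separate conflict.

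**Conclusion.** The point holds as an inconsistency that should be fixed before the data are summarised. Section 7.6, read literally, contradicts the Section 7 definition of the control group and makes membership of a randomised group depend on events after randomisation. The Synopsis leaves open whether stoppers are counted with controls or dropped. Either course can bias the group summaries and confidence intervals of change, whereas follow-up only, summarised as randomised, would not.

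Neither the size nor the direction of any bias can be known from the protocol. The ranges of 0.04 to 0.25 SD and 0.09 to 0.54 SD show what is possible under the assumed stopping rate, deficit and absence of a true effect. They are not estimates for this trial.

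**What to change.** - **Section 7.6.** Delete the clause on admission to the control group, or state that it refers only to follow-up without training. Add: *Patients who stop training but remain in the study are summarised in the group to which they were randomised.*
- **Synopsis, analysis sets.** Replace the definition with: *Full Analysis Set: all randomised patients, in the group to which they were randomised. Patients who complete nine months as assigned form a supplementary set.* This also removes the conflict with the sentence that includes all participants.
- **Appendix A.** State which assessment schedule applies to patients who stop training. At the same time, reconcile the Synopsis (six lung function tests for all patients) with the group 3 table (three). Which schedule is appropriate is for the investigators to decide.

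The cost is wording in a protocol amendment, with no new patients. The downsides are that training-arm results may look slightly less favourable and that group 3 gains no extra patients. When training should stop is a clinical matter and is not addressed here.
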